4.3 Reactogenicity and safety populations

Population	Description
Healthy safety	
All eligible participants who
 
 ● generally healthy without any major immunocompromise ● received at least one dose of the vaccine ● has proven seronegative or unknown at baseline and not known to be infected ● reported any safety or reactogenicity data
All safety	
All eligible participants who
 
 ● received at least one dose of the vaccine ● reported any safety or reactogenicity data

5 Methodology and hypotheses

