3.1 Primary endpoints

3.1.1 Reactogenicity endpoints

3.1.1.1 Adverse reactions

For all participants receiving one dose or more under our study protocol, excluding those who already completed immunization prior to joining the study, we solicit prespecified local and systemic reactions for 7 days after immunization with each dose (days 0 to 7). Participants are asked to report these reactions daily and will be reminded if they missed reporting.

Solicited reactions are either local or systemic, and they include:

- Pain at injection site
- Pruritus at injection site
- Swelling, erythema and induration at injection site
- Headache
- Fatigue
- Myalgia
- Nausea
- Diarrhea
- Vomiting
- Arthralgia
- Cough
- Chills
- Fever
- Decreased appetite
- Rhinorrhea
- Nasal congestion
- Sore throat
- Abdominal pain

For listed reactions that are present, participants are to fill in related information as specified for the reaction (fever and swelling, erythema and induration at injection site), or determine the severity according to the following scale:

1. Mild: tolerable, not affecting daily activities
2. Moderate: performance of some daily activities affected
3. Severe: performance of some daily activities prevented

For fever, we determine the severity according to body temperature reported by participant:

1. Mild: 38.0-38.4 degrees Celsius
2. Moderate: 38.5-38.9 degrees Celsius
3. Severe: 39.0 degrees Celsius or higher

For swelling, erythema and induration at injection site, we determine the severity according to the following:

1. Mild: diameter 2.0 to 4.9 cm
2. Moderate: diameter 5.0 to 9.9 cm
3. Severe: diameter 10.0 cm or longer

We analyze the presence and absence of each adverse reaction by maximum severity and use of antipyretic medication on any day from days 0-7 after each dose.

- Presence on any day refers to reported presence on any day between days 0-7.
- Absence on any day refers to no reported presence on any day between days 0-7, either reported absence on all days or reported absence on any day and missing report on other days.
- Missing refers to a continued missing report on all days between days 0-7

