3.2 Secondary endpoints

3.2.1 Adverse events

For all participants receiving one dose or more under our study protocol, excluding those who already completed immunization prior to joining the study, we evaluate unsolicited, volunteered local and systemic adverse events for 28 days after immunization with each dose (days 0 to 28) before receipt of the next dose (at least 21 days for BNT162b2 first dose).

For all participants receiving one dose or more under our study protocol, including those who already completed immunization prior to joining the study, we evaluate unsolicited, volunteered severe adverse events from joining the study, until 36 months after completing immunization. Severe adverse events are defined as adverse events involving any of the following conditions.

1. Hospitalization
2. Life-threatening illness
3. Death
4. Disability or permanent damage, including birth defect of participants' offspring

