4.1 Total enrolled population

Population	Description
Enrolled	All participants with a signed informed consent form, screened in as included by study physician and received at least one dose of study vaccine

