6.2 Secondary endpoints

6.2.1 Adverse events

We analyze unsolicited adverse events based on the following:

- Estimand: Percentage of participants reporting an adverse event (by medDRA terms)
- Analysis set: (healthy) safety population

- Time-point: after each dose on days 0-28, before the next dose
- Statistics: incidence (events per person), n and N

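### The safety sets require that a participant reported something, so the denominator for volunteered adverse events drops silent participants and the percentage can only rise relative to all dosed

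*SAP*

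**What the plan says.** Section 4.3 defines a healthy and an all-participant safety set. Both ask for at least one vaccine dose and, as a further condition, that the participant "reported any safety or reactogenicity data". Section 4.1 already defines a dosed population without that condition: people who consented and were "screened in as included by study physician and received at least one dose of study vaccine".

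For unsolicited adverse events, section 6.2.1 gives a percentage of participants over days 0-28 after each dose, with n and N, and states "Analysis set: (healthy) safety population". Section 3.2.1 treats these events as volunteered.

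Section 3.2.1 also extends collection of severe events beyond that window: "we evaluate unsolicited, volunteered severe adverse events from joining the study, until 36 months after completing immunization". This includes people who were fully immunised before joining. The same section leaves them out of the day 0-28 events, and section 3.1.1.1 leaves them out of the diary: "excluding those who already completed immunization prior to joining the study, we solicit prespecified local and systemic reactions for 7 days".

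For solicited reactions, section 3.1.1.1 says "Participants are asked to report these reactions daily and will be reminded if they missed reporting". Absence is itself a reported state ("either reported absence on all days or reported absence on any day and missing report on other days"), while "Missing refers to a continued missing report on all days between days 0-7".

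**The concern.** A solicited reaction has three states: present, absent and missing. A volunteered event has only two: reported, or nothing heard. When the set asks for some report before a person counts, someone with a diary entry is in the set whatever happened later. Someone with no diary entry is in only if there was an event to volunteer. In that second group, entry to N depends on the outcome being measured.

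At stake is the unsolicited-event percentage, in total and in the disease subgroups, whose safety is described separately at interim analyses 1 and 4. If diary completion differed between vaccines or disease groups, the inflation would differ too. The SAP also collects severe events from people who are never asked for a diary, and section 4.3 gives the only sets named for safety.

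**Working it through.** **The plan's own figure nearby.** Section 5.1.2 says 110 adolescents give a precision of 7.5 points at 80% prevalence: 1.96 × √(0.8 × 0.2 / 110) = 7.48 points. This is reproduced, and nothing below changes it. The target of 120 allows (120 − 110)/120 = 8.3% attrition. The set definition itself carries no figure.

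**Who is counted for unsolicited events** (sections 3.1.1.1, 3.2.1 and 4.3 read together):

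| Dosed, diary-eligible participant | Volunteers an event | Volunteers none |
|---|---|---|
| At least one diary entry after any dose | in n and N | in N |
| No diary entry after any dose | in n and N | not in N |

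Only the last cell is lost, and it holds no recorded event. The numerator is therefore the same as for all dosed participants, and only N shrinks.

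**Formula.** Let m be the share of dosed participants with no diary entry, p the event risk (equal in both parts), and v the chance that a no-diary participant volunteers an event. All three are assumptions. Diary filers are taken to report every event.

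- All-dosed percentage: p(1 − m + mv)
- Safety-set percentage: p(1 − m + mv) / (1 − m + mpv)
- Ratio of the two: 1/(1 − m + mpv), which is never below 1 and never above 1/(1 − m). The bound is 1/0.95 = 1.05 at m = 5% and 1/0.80 = 1.25 at m = 20%.

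**Full volunteering (v = 1), 120 dosed.** The all-dosed percentage equals p.

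| m | Set N at p = 5% | Set percentage | Set N at p = 10% | Set percentage |
|---|---|---|---|---|
| 5% | 114 + 0.3 = 114.3 | 6/114.3 = 5.25% | 114 + 0.6 = 114.6 | 12/114.6 = 10.47% |
| 8.3% | 110 + 0.5 = 110.5 | 6/110.5 = 5.43% | 110 + 1.0 = 111.0 | 12/111.0 = 10.81% |
| 10% | 108 + 0.6 = 108.6 | 6/108.6 = 5.52% | 108 + 1.2 = 109.2 | 12/109.2 = 10.99% |
| 20% | 96 + 1.2 = 97.2 | 6/97.2 = 6.17% | 96 + 2.4 = 98.4 | 12/98.4 = 12.20% |

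**No volunteering (v = 0).** The set percentage is p, so it is unbiased. The all-dosed figure is p(1 − m): at p = 5% and m = 20%, 4.0%.

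**Half volunteering (v = 0.5), p = 5%, m = 20%.** n = 4.8 + 0.6 = 5.4. The set gives 5.4/96.6 = 5.59%; all dosed gives 5.4/120 = 4.50%.

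**Against sampling error.** Hold six recorded events fixed and vary only how many dosed people fall outside the set. The Clopper-Pearson 95% intervals are 6/120 = 5.0% (1.9 to 10.6), 6/110 = 5.5% (2.0 to 11.5) and 6/96 = 6.3% (2.3 to 13.1). The shift is small beside the interval width.

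**Severe events to 36 months.** People immunised before joining are outside both the diary and the day 0-28 collection. If these sets were used for such a percentage, m in that group would approach 1 and the bound 1/(1 − m) would no longer limit the inflation. Section 6.2.1 defines no such percentage, so no size is attached.

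**The case against.** The best defence is that the condition selects on reporting, not on having an event. Diary-eligible participants are asked every day and reminded, and one entry of absence after any dose is enough to qualify. Only people who never make an entry are lost. This stands, and it confines the point to volunteered events in participants with no diary.

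The defence adds that upward bias against the true rate needs silent participants to volunteer their events anyway. If they do not, the set is unbiased and an all-dosed denominator is too low. This also stands. What is certain is the direction relative to all dosed participants, not relative to the truth.

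It is also true that section 6.4.2.2 tabulates who submitted data in the enrolled and healthy safety populations, so the loss will be visible. That allows an approximate check but does not correct the reported percentage. Nor does the SAP say whether a no-event answer at a clinic visit counts as safety data. If it does, fewer people are lost.

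Three stronger readings may tempt a reader:

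- *Solicited reactions are inflated in the same way.* They are not. Leaving out people with no diary agrees with the missing rule in section 3.1.1.1, and counting them as reaction-free would bias those percentages down.
- *Because one set serves every dose, people never given dose 2 or 3 dilute the later reaction percentages.* Section 3.1.1.1 needs at least one reported absence before a person counts as absent, so someone not given that dose cannot be coded reaction-free.
- *People immunised before joining already produce a meaningless severe-event rate.* Section 6.2.1 analyses only days 0-28, a window that excludes them, so there is no specified rate to be wrong.

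**Conclusion.** The point holds for unsolicited, volunteered adverse events. As written, the denominator keeps a no-diary participant with a volunteered event and discards one without, so the percentage cannot fall below the all-dosed figure and can exceed it by a factor of up to 1/(1 − m). For an assumed m of 5% to 20%, a true 5% reads as about 5.2% to 6.2% under full volunteering and stays at 5% under none. These sizes rest on assumed values of m, p and v, because the SAP gives no non-reporting rate. A difference in bias between vaccines is possible, but nothing in the document shows one. For severe events the weakness is latent: it would become serious only if the section 4.3 sets were used for a percentage to 36 months. The effect is modest, but worth correcting because a suitable dosed population is already defined.

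**What to change.** In sections 4.3 and 6.2.1, remove the reporting condition for unsolicited and severe events. Take as N all participants with at least one dose, that is, the Enrolled set of section 4.1 with the healthy restriction where needed. For days 0-28, limit N to those who received the dose in question under the protocol. If severe events to 36 months are summarised, show people immunised before joining separately, with follow-up counted from joining. Section 4.1 asks for a dose of study vaccine, so say explicitly that this group is included.

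In section 6.1.1.1, state that N for solicited reactions is those with at least one diary entry for that dose, in line with section 3.1.1.1. Show beside it, by vaccine, how many recipients of that dose had no diary.

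The cost is wording in sections 4.3, 6.1.1.1 and 6.2.1. No new data are needed and no sample-size figure changes. The downside is that participants who volunteer nothing are counted as event-free, which understates the rate if some had events they did not report. The no-diary counts let a reader judge how much that matters.

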5.1 Hypotheses and decision rules

5.1.1 Immunogenicity hypothesis

A primary objective of the study is to prove or disprove the hypothesis that immunogenicity of either vaccines are non-inferior in healthy adolescents/children to that in healthy adults at the acute dose 2 timepoint (around 1 month post-dose 2). We test the hypothesis in two-dose and three-dose healthy evaluable immunogenicity populations for each of the following specified tests.

$$H_0: \ln(\mu_2) - \ln(\mu_1) < \ln(0.6)$$

$\ln(0.6)$ refers to a non-inferiority margin of 1.67 fold, while $\ln(\mu_2)$ and $\ln(\mu_1)$ refer to the natural log of the geometric mean of the following immunogenicity assessments performed at the acute dose 2 timepoint from recipients of respective vaccines aged between 5-10 or 11-17 years and 18 or above. If the lower limit of the 95% confidence interval for mean ratio is ≥ 0.6 , the respective non-inferiority objective is met.

1. Anti-S binding antibody level
2. Anti-S-RBD binding antibody level
3. Surrogate neutralizing antibody inhibition level
4. Neutralizing antibody titer
5. Anti-S antibody avidity index
6. Anti-S FcgRIIIa-binding antibody level
7. Total responsive Th1 (to S, and N and M if applicable)
8. Total responsive Tc1 (to S, and N and M if applicable)
9. Anti-N binding antibody level
10. Anti-N-CTD binding antibody level

In addition, we also test a hypothesis that immunogenicity of a single dose of BNT162b2 in adolescents is non-inferior to that of two doses of BNT162b2 in adults.

For healthy children and adolescents receiving intradermal vaccination, we test also a second hypothesis that superior immunogenicity outcomes can be detected in intradermal route over intramuscular route in participants of the same age group, as well as for non-inferiority.

$$H_0: \ln(\mu_2) - \ln(\mu_1) \leq \ln(1)$$

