6.1.2.9 GMR of S and S-RBD binding IgG, surrogate neutralizing antibody inhibition level, and neutralizing antibody titers, IgG avidity index and FcγRIIIa-binding IgG in participants 11-17 years of age receiving 2 doses of BNT162b2 to those receiving 2/3 doses of CoronaVac

- Estimands: geometric mean ratio
- Analysis set: 2/3-dose evaluable and expanded immunogenicity populations
- Time points: 1 month after dose 2, 2 weeks after dose 3, 6, 18 and 36 months after vaccination; including cross-comparison of two doses of BNT162b2 and three doses of CoronaVac
- Statistics: exponentiated difference in mean and CI95 on natural log scale for geometric means and two-sided CI95 (or one-sided CI97.5).
- Figure: forest plot
- Intercurrent events: Values below the cut-off/lower limit of detection/quantification may be set to 0.5 of the cut-off/limit for analysis if applicable for the assay.

6.1.2.10 GMR of total S responsive Th1 and Tc1 cell frequencies in participants 11-17 years of age receiving 2 doses of BNT162b2 to those receiving 2/3 doses of CoronaVac

- Estimands: geometric mean ratio
- Analysis set: 2/3-dose evaluable and expanded immunogenicity populations
- Time points: 1 month after dose 2, 2 weeks after dose 3, 6, 18 and 36 months after vaccination; including cross-comparison of two doses of BNT162b2 and three doses of CoronaVac

- Statistics: exponentiated difference in mean and CI95 on natural log scale for geometric means and two-sided CI95 (or one-sided CI97.5).
- Figure: forest plot
- Intercurrent events: Values below the cut-off/lower limit of detection/quantification may be set to 0.5 of the cut-off/limit for analysis if applicable for the assay.

6.1.2.11 GMR of S and S-RBD binding IgG, surrogate neutralizing antibody inhibition level, and neutralizing antibody titers, IgG avidity index and FcgRIIIa-binding IgG in participants receiving intradermal CoronaVac to intramuscular CoronaVac

- Estimands: geometric mean ratio
- Analysis set: 2/3-dose evaluable and expanded immunogenicity populations
- Time points: 1 month after dose 2, pre-dose 3, 2 weeks after dose 3, 6, 18 and 36 months after vaccination
- Statistics: exponentiated difference in mean and CI95 on natural log scale for geometric means and two-sided CI95 (or one-sided CI97.5).
- Figure: forest plot
- Intercurrent events: Values below the cut-off/lower limit of detection/quantification may be set to 0.5 of the cut-off/limit for analysis if applicable for the assay.

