6.1.2.12 GMR of total S, N and M responsive Th1 and Tc1 cell frequencies in participants 11-17 years of age receiving intradermal CoronaVac to intramuscular CoronaVac

- Estimands: geometric mean ratio
- Analysis set: 2/3-dose evaluable and expanded immunogenicity populations
- Time points: 1 month after dose 2, pre-dose 3, 2 weeks after dose 3, 6, 18 and 36 months after vaccination
- Statistics: exponentiated difference in mean and CI95 on natural log scale for geometric means and two-sided CI95 (or one-sided CI97.5).
- Figure: forest plot
- Intercurrent events: Values below the cut-off/lower limit of detection/quantification may be set to 0.5 of the cut-off/limit for analysis if applicable for the assay.

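### The intradermal superiority hypothesis fixes no deciding outcome, visit or criterion, so one positive contrast among many could be reported as a route advantage

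*SAP*

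**What the plan says.** Section 5.1.1 states two kinds of hypothesis. The first is age bridging: immunogenicity is to be "non-inferior in healthy adolescents/children to that in healthy adults at the acute dose 2 timepoint (around 1 month post-dose 2"). It has a visit, a numbered list of assessments and a decision rule: "If the lower limit of the 95% confidence interval for mean ratio is" at least 0.6, the objective for that assessment is met.

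The second concerns route. For healthy children and adolescents vaccinated intradermally, the SAP also tests that "superior immunogenicity outcomes can be detected in intradermal route over intramuscular route in participants of the same age group, as well as for non-inferiority". The null is that the log difference is at most ln(1), that is, GMR ≤ 1. No visit, outcome or superiority criterion follows. The symbols μ1 and μ2 are reused, but section 5.1.1 defines them only by age group.

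The contrasts for this comparison are in section 6.1, Primary analysis. Section 6.1.2.11 covers "S and S-RBD binding IgG, surrogate neutralizing antibody inhibition level, and neutralizing antibody titers, IgG avidity index and FcgRIIIa-binding IgG in participants receiving intradermal" versus intramuscular CoronaVac. Section 6.1.2.12 is the "GMR of total S, N and M responsive Th1 and Tc1 cell frequencies in participants 11-17 years of age receiving intradermal CoronaVac" versus intramuscular. Both list the same visits: "1 month after dose 2, pre-dose 3, 2 weeks after dose 3, 6, 18 and 36 months after vaccination". Both give the same statistic: "exponentiated difference in mean and CI95 on natural log scale for geometric means and two-sided CI95 (or one-sided CI97.5"). The age comparison in 6.1.2.7 and 6.1.2.8 adds a note tying the non-inferiority test to one month after dose 2. The route comparison has no such note. Section 5.1.3 says multiplicity is not considered.

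**The concern.** A superiority hypothesis should say beforehand which result would establish it and which would not. This one says only that superior outcomes can be detected. If antibody binding were higher by the intradermal route two weeks after dose 3 but not one month after dose 2, or if Th1 were higher and neutralizing titer were not, the SAP gives no way to decide whether the hypothesis is met. Someone reporting the trial could pick the favourable contrast and still be within the plan. The stake is a claimed route benefit that arose by chance, at well above the nominal 2.5%.

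**Working it through.** **What the SAP fixes for each hypothesis**

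| Element | Age bridging | Route superiority |
|---|---|---|
| Groups behind μ1, μ2 | defined by age (5.1.1) | not redefined |
| Visit | acute dose 2 (5.1.1; repeated in 6.1.2.7–6.1.2.8) | none; six visits in 6.1.2.11–6.1.2.12 |
| Outcome rule | each listed assessment has its own objective | none |
| Criterion | lower 95% limit ≥ 0.6 | none |

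The SAP states no error rate for the route comparison, so there is no figure of its own to reproduce on this point. The sample-size text in 5.1.2 covers children versus adults and vaccine types, not route.

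**Inputs**
- Outcomes: S IgG, S-RBD IgG, surrogate neutralization, neutralizing titer, avidity and FcγRIIIa binding (six, from 6.1.2.11), plus Th1 and Tc1 (two, from 6.1.2.12). Total 8.
- Visits: 6.
- Contrasts: 8 × 6 = 48.
- Level: a two-sided 95% CI, or a one-sided 97.5% CI, gives 0.025 in the direction of intradermal benefit.
- Correlation between test statistics: not in the SAP. Assumed at 0.5, with a range of 0.8 to 0.3, and independence as a reference.

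**Independent tests.** The chance of at least one false superiority is 1 − (1 − 0.025)^k.
- k = 8: 1 − 0.975^8 = 18.3%.
- k = 48: 1 − 0.975^48 = 70.3%.

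**Correlated tests.** Normal test statistics were simulated under no route difference. The correlation matrix was the product of an equicorrelated outcome part and an equicorrelated visit part, with the same value in both. The result is the proportion of draws whose largest statistic exceeds 1.96.

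| Contrasts counted | Correlation 0.8 | 0.5 | 0.3 | Independent |
|---|---|---|---|---|
| 8 outcomes, 1 visit | 8% | 13% | 15% | 18% |
| 8 outcomes, 2 visits | 12% | 21% | 27% | 33% |
| 8 outcomes, 6 visits | 19% | 40% | 54% | 70% |

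(The independent figure for two visits is 1 − 0.975^16 = 33.3%.)

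**The count is not inflated.** It uses the evaluable sets only, although the expanded sets are also analysed (6.1.2). It counts neutralizing titer once, although 3.1.2.3 measures both 50% and 90% titers. It leaves out N and N-CTD IgG, which are on the list in 5.1.1.

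**With the gap closed.** One named outcome at one named visit gives 2.5%. For eight outcomes at one visit, Holm starts at 0.025 / 8 = 0.3125% one-sided and keeps the family at no more than 2.5%.

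**The case against.** Several counter-arguments have weight.

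- **The visit may carry over.** The superiority null reuses μ1 and μ2, which 5.1.1 ties to the acute dose 2 timepoint. Taking that visit across is a natural reading, and it gives about 13%, not 40%. This stands as a reason to lead with the lower figure. It leaves eight outcomes undecided.
- **The later visits may fall outside the primary sets.** Section 4.2 defines the two- and three-dose evaluable sets by samples in the acute windows after dose 2 or dose 3. Read literally, that leaves two visits, or about 21% (12–27%). Yet 6.1.2.11 and 6.1.2.12 name these sets together with all six visits, so the SAP does not settle the matter.
- **Sections 6.1.2.11–6.1.2.12 may be estimation only.** They ask for GMRs, intervals and a forest plot and do not mention a test. But 5.1.1 does state a test, these are the contrasts that bear on it, and none is labelled descriptive.
- **Each outcome may carry its own claim at 2.5%**, as the age objectives do. That is possible, and the SAP contains no explicit rule that one success proves an overall route benefit. It contains no rule against it either.
- **The route question is not pivotal.** None of the objectives in 2.1 mentions route, and no interim analysis in section 7 names it. This limits the weight of the point.

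A reader might infer that 40% is the most the error could be, or that it is the error the plan implies. Neither holds. It is a mid-range value that needs all six visits to count and an assumed correlation of 0.5; weaker correlation raises it, and fewer visits lower it.

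**Conclusion.** The concern holds as a gap in the definition of the hypothesis. The route superiority test has no deciding outcome, visit or criterion, and the multiplicity of the contrasts that could satisfy it is expressly left aside. With no true difference, the chance of at least one superior result is about 13% on the narrower reading of eight outcomes at the acute dose 2 visit (8–15%; 18% if independent). On the widest reading of eight outcomes at six visits it is about 40% (19–54%; 70% if independent). The nominal level is 2.5%. All the correlated figures rest on correlations assumed here, and all the figures apply if any single positive contrast is reported as a route advantage. The SAP does not command that reporting; it fails to exclude it. The point should be corrected, but it does not touch the age-bridging tests.

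**What to change.** In section 5.1.1:
- define μ1 and μ2 by route for this hypothesis;
- fix the superiority test at the acute dose 2 timepoint in the two-dose healthy evaluable population;
- state the criterion: lower limit of the two-sided 95% CI for the intradermal-to-intramuscular GMR above 1.

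Then choose one of two routes to a single claim. Either name one deciding outcome in advance (S-RBD IgG is an example; nothing in the SAP ranks it above the others, and the sponsor may choose another listed outcome). Or apply Holm across the eight outcomes at that visit, in which case the Holm-adjusted one-sided p-value below 0.025 replaces the unadjusted interval as the criterion.

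Putting non-inferiority first as a gate is not needed for error control: a lower limit above 1 already exceeds 0.6.

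In 6.1.2.11 and 6.1.2.12, label all other outcomes and visits as descriptive, with GMR and 95% CI. Amend 5.1.3 to match.

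The cost is SAP wording only. With one named outcome, the other outcomes and visits can no longer carry a superiority claim. With Holm, all eight outcomes can do so at the chosen visit, each with somewhat less power. The SAP states no power for the route comparison, so the size of that loss cannot be given from the document.
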